### **Duration of response**

Patients who are neither complete nor partial responders will not be included in the analysis of the duration of response. Complete and partial responders who did not relapse at the data cut-off date will be censored at the date of the last assessment of response with a known outcome.

Patients who are not complete responders will not be included in the analysis of the duration of complete response. Complete responders who did not change to PR or relapse at the data cut-off date will be censored at the date of the last assessment of response with a known outcome.

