12.5.1 Efficacy and/or Pharmacodynamic endpoint(s)

For all secondary efficacy endpoints, the FAS will be used.

CR rate at Week 13, Week 52 and yearly after

The number and percentage of participants who meet the hematological CR criteria (at Week 13, Week 52 and yearly after respectively, see [Section 8.3](#) for definition of response) will be presented and 2-sided Exact binomial 95% (Clopper-Pearson) confidence interval will be reported. For missing values and discontinuations, a similar approach will be adopted as for the primary endpoint.

Overall response (CR+PR) rate at Week 13, Week 26, Week 52 and yearly after

Hematologic overall response rate at specific visit is defined as percentage of participants who achieved hematologic response (see [Section 8.3](#)) at specific visit in FAS. The number and percentage of participants who meet the hematological overall response criteria (at Week 13, Week 26, Week 52 and yearly after respectively) will be presented and 2-sided Exact binomial 95% (Clopper-Pearson) confidence interval will be reported. For missing values and discontinuations, a similar approach will be adopted as for the primary endpoint.

Duration of response

For participants who responded, duration of response will be defined as the time from the first date of a response until the first date of relapse or death, which occurs first. Participant still responding at the cut-off date will be censored at date of last response assessment. Only participants with at least 2 response assessments are included in the duration of response, unless they relapsed or died. Duration of response will be estimated using Kaplan-Meier method and will be plotted.

Transfusion-free interval before Week 13 and Week 26

For platelet transfusion, transfusion-free interval is defined as the time from most recent platelet transfusion to the date of response assessment. Only participants with response assessments at specific visits (Week 13 or 26) are included in the transfusion-free interval. Descriptive statistics including mean, SD, median, 25th and 75th quartiles, minimum, and maximum will be summarized for the transfusion-free interval. The same analysis applies to RBC transfusion. The analysis will be presented for participants with CR, PR and NR.

Proportion of participants who becomes transfusion independent

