**Table 1-1 Objectives and related endpoints**

Objective(s)	Endpoint(s)
Primary objective(s)	Endpoint(s) for primary objective(s)

To evaluate the efficacy of eltrombopag in combination with r-ATG and CsA in terms of complete response rate at 6 months in East-Asian patients with treatment naive severe aplastic anemia (SAA)

	

CR rate at Week 26 (6 months) after starting the study treatment

Secondary objective(s)	Endpoint(s) for secondary objective(s)

To evaluate complete response rate at 3, 12 months and yearly after

To evaluate overall response rate at 3, 6, 12 months and yearly after

To evaluate duration of response

To evaluate overall survival (OS)

	

CR rate at Week 13 (3 months), Week 52 (12 months) and yearly after

Overall response (CR+PR) rate at Week 13 (3 months), Week 26 (6 months), Week 52 (12 months) and yearly after

Time from the date of the start of response to the date of relapse or death, whichever occurs first at any time during the study

Time from the date of first dose of study treatment to the date of death

Objective(s)	Endpoint(s)
	

Overall survival rate at Week 26, Week 52 and yearly after

To evaluate the need for transfusion (packed RBC units and platelet units)

	

Time from the most recent transfusion to Week 13 and Week 26

Proportion of subjects who becomes (platelet/RBC) transfusion independent

To evaluate safety and tolerability of eltrombopag in combination with r-ATG and CsA

	

Frequency and severity of AEs, severe adverse events (SAEs), vital signs, electrocardiogram and laboratory abnormalities

To evaluate clonal evolution

	

Time from the date of first dose of study treatment to the date of first occurrence of any of the clonal evolution events

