### **Duration of response**

Duration of response will be derived as the time from first documented and confirmed response (either CR or PR) until the time of relapse or death whichever occurs first. Both the responses and the relapse will be programmatically derived. Patients who are neither complete nor partial responders will not be included in the analysis of the duration of response.

Duration of complete response will be similarly derived for patients who had a complete response. Patients who are not complete responders will not be included in the analysis of the duration of complete response.

Clinical relapse is considered as the occurrence of any of the following event in a subject who had achieved a hematological response (CR or PR) but has subsequently lost response (not explained by any other independent concomitant medical conditions) in one blood count measurements:

- meeting again the criteria for SAA, equivalent to patients with at least two of the following parameters in peripheral blood.
  - Absolute neutrophil count  $< 0.5 \times 10^9/L$
  - Platelet count  $< 20 \times 10^9/L$
  - Absolute reticulocyte count  $< 20 \times 10^9/L$
- requirement for transfusion again for subjects who had been transfusion independent
- decrease in any of the peripheral blood counts to: absolute neutrophil count  $< 0.5 \times 10^9/L$  or platelets  $< 20 \times 10^9/L$ .

The analysis of duration of response will be based on response assessment which are derived programmatically using laboratory results instead of those reported in the response assessment CRF.

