### **Duration of response**

Kaplan-Meier curve of the duration of response and duration of complete response will be constructed, and the quartiles of the survival function will be provided along with 95% confidence interval. Kaplan-Meier estimates with 95% confidence intervals every 3 months will be summarized as well.

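### SAP 2.7.3 leaves death out of the censoring rule for duration of response and disagrees with 2.7.1 on what ends a complete response; programmed literally, it would overstate the curve if any responder dies in response

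*SAP*

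**What the plan says.** Death is an event wherever the endpoint is defined. SAP Table 1-1 measures duration of response from its start "to the date of relapse or death, whichever occurs first at any time during the study", as does protocol Table 2-1. SAP 2.7.1 runs it "until the time of relapse or death whichever occurs first". Protocol 12.5.1 defines it as "the time from the first date of a response until the first date of relapse or death". The final-analysis SAP repeats the SAP text.

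The protocol's censoring rule fits that definition: "Participant still responding at the cut-off date will be censored at date of last response assessment". Protocol 12.5.1 also requires at least two response assessments for inclusion, but waives this for participants "unless they relapsed or died", so it expects deaths to contribute.

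The SAP censoring rule in 2.7.3 is worded differently. For duration of response: "Complete and partial responders who did not relapse at the data cut-off date will be censored", at the last response assessment with a known outcome. For duration of CR: "Complete responders who did not change to PR or relapse at the data cut-off date will be censored", at the same point. Neither sentence mentions death. On CR, 2.7.1 says only that the duration is derived in a similar way. Both sentences recur unchanged in 2.7.3 of the final-analysis SAP.

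Section 4 of each SAP, on changes from the protocol, lists added endpoints only. It declares no change to the events or censoring of this endpoint.

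**The concern.** A responder who dies without relapsing has an event at death under 2.7.1, and is censored at the last assessment before death under the literal words of 2.7.3. Both cannot be programmed. The literal 2.7.3 rule would estimate time to relapse with death treated as uninformative censoring, which is not the protocol endpoint.

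Duration of CR has a further gap. For a complete responder who falls to PR without relapsing, 2.7.3 implies that the CR has ended. A derivation parallel to duration of response under 2.7.1 would count only relapse or death. The curve therefore depends on which section the programmer follows, and no full event list exists to settle it.

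The SAP states that "Kaplan-Meier curve of the duration of response and duration of complete response will be constructed", with quartiles and three-monthly estimates. With few responders, one reclassified patient can shift these visibly. Duration of response is not among the analyses that the final-analysis SAP says it will not repeat, so the wording also governs follow-up to Year 3.

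**Working it through.** **Step 1: compare the rules.** The plan gives no figure for duration of response, so there is none to reproduce. The first check sets the two sections side by side.

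| Patient, at cut-off | SAP 2.7.1 | SAP 2.7.3, literal | Protocol 12.5.1 |
|---|---|---|---|
| Responder, relapsed | event | not censored | event |
| Responder, alive, no relapse | no event | censored | censored if still responding |
| Responder, died without relapse | event | censored | event |
| Complete responder, now PR, no relapse | no event, if derived in parallel | not censored, so an ending is implied | duration of CR not defined |

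The third and fourth rows conflict.

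**Step 2: size of the conflict over death.** The documents do not give the number of responders (n), relapses (r) or deaths in response (d). The only limit is the planned enrolment of about 36. Assumed ranges: n = 18 or 24, r = 4 or 8, d = 0 to 3; relapse and death times uniform over 1 to 24 months from response; everyone else followed beyond 24 months; assessments at about 0, 3, 9 and 21 months after response.

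With nobody else censored before 24 months:

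- deaths counted: S(24) = 1 − (r + d)/n
- deaths censored: S(24) lies between 1 − r/(n − d), if all are censored before the first relapse, and 1 − r/n, if all are censored after the last.

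Example with n = 24, r = 4, d = 1. Counted: 19/24 = 79.2%. Censored: between 19/23 = 82.6% and 20/24 = 83.3%.

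Averaging over 4,000 simulated data sets per row gives the 24-month estimate with deaths counted / deaths censored, and the excess in points (taken before rounding):

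| n, r | 1 death | 2 deaths | 3 deaths |
|---|---|---|---|
| 18, 4 | 72.2 / 76.8, +4.6 | 66.7 / 75.8, +9.1 | 61.1 / 74.6, +13.5 |
| 18, 8 | 50.0 / 53.5, +3.5 | 44.4 / 51.3, +6.9 | 38.9 / 48.8, +9.9 |
| 24, 4 | 79.2 / 82.8, +3.7 | 75.0 / 82.3, +7.3 | 70.8 / 81.7, +10.8 |
| 24, 8 | 62.5 / 65.6, +3.1 | 58.3 / 64.4, +6.1 | 54.2 / 63.2, +9.0 |

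With no deaths the two estimates coincide in every row.

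**Step 3: effect on a quartile.** Take n = 18, r = 4, d = 1. Counted: 13/18 = 72.2%, so the first quartile is reached by 24 months. Censored: between 13/17 = 76.5% and 14/18 = 77.8%, so it is not reached, whenever the death occurred.

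**Step 4: direction.** From the date of death onward, the censored version is the higher one. Between the last assessment and the death it can be marginally lower, because the patient leaves the risk set early. For example, with 24 responders and one relapse in that gap, 22/23 = 95.7% against 23/24 = 95.8%. The overstatement therefore concerns the curve from the death onward.

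No size is given for the change-to-PR conflict, since the documents offer nothing on how often it would occur.

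**The case against.** The strongest reply is that 2.7.3 is shorthand. Censoring applies to patients without an event, and a responder who died already has an event date under 2.7.1. Death is named in the protocol's objectives table and section 12.5.1, in SAP Table 1-1 and in SAP 2.7.1. Section 2.7.3 concerns missing values, censoring and discontinuations and does not claim to redefine the endpoint. A careful programmer would count the death, and the curve would be right.

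Much of this stands. A reader might infer that the planned curve is biased, that 2.7.3 prevails over 2.7.1, or that the SAP deliberately dropped death. The documents support none of these. Neither section is ranked above the other, section 4 of each SAP declares no such change, and the bias is zero if no responder dies in response or if 2.7.1 is followed.

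The wording conflict remains. The overall survival rule in the same 2.7.3 makes its death condition explicit, while the duration-of-response rule does not. Response and relapse are to be derived by program, so the written rule matters. The shorthand reading also does not resolve duration of CR, where 2.7.3 implies an event that 2.7.1 does not list.

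**Conclusion.** The censoring sentences are wrong as written. They conflict with the event definition in the protocol and in SAP 2.7.1, and the duration-of-CR events are not consistently specified. High confidence applies to that mismatch.

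A numerical bias is conditional on two things: literal programming of 2.7.3 and at least one death in response. Under the assumed ranges, the average 24-month excess is 3.1 to 4.6 points with one death, 6.1 to 9.1 with two and 9.0 to 13.5 with three. These are illustrations, not predictions for this trial.

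The reach is limited. Duration of response is a secondary, descriptive endpoint in a single-arm study without formal testing. The primary CR rate does not use this rule, and overall survival counts deaths from any cause under its own rule.

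**What to change.** In section 2.7.3 of both SAPs, replace the duration-of-response sentence with wording such as: *Responders who have neither relapsed nor died by the cut-off date will be censored at the date of the last response assessment with a known outcome.*

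Add death to the duration-of-CR sentence in the same way. In 2.7.1, replace the reference to a similar derivation with the full list of events that end a CR, stating whether change to PR is one, and make 2.7.3 match it.

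If outputs already exist, confirm how any death in response was coded and rerun the curves, quartiles and three-monthly estimates if it was censored.

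The cost is a few words in two paragraphs of 2.7.3 and a short event list in 2.7.1, in each SAP. No new data are needed.

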8.3 Efficacy

Efficacy assessments include hematologic results, transfusion data, assessment of relapse and survival.

Hematologic parameters will be assessed at Screening, weekly from Week 1 to Week 8, then every 2 weeks to Week 26 (weekly until stabilization of the dose), then every 4 weeks until the end of eltrombopag treatment (every 2 weeks until stabilization of the dose) and yearly during the post-treatment follow-up (up to Year 3). Hematologic parameters will also be assessed as per the investigator decision to assess the maintenance of the response, relapse or for safety reasons.

Transfusion data will be recorded for any transfusion administered during the 60 days prior to treatment start and until the end of eltrombopag treatment for all participants who discontinue eltrombopag due to non-response at W26, relapse or alternative SAA treatment, and until the completion of study follow up for all the other participants. The date and time, content and number of units of each transfusion will be recorded.

Relapse will be determined according to the definition in this section by investigator and will be recorded into eCRF.

All participants will be followed for survival status every 3 months regardless of treatment discontinuation reason up to Year 3 until study completion, death, lost to follow-up, or withdrawal of consent for survival follow-up. Survival information can be obtained via phone, and information will be documented in the source documents and relevant eCRFs.

Hematologic response assessment will be performed by investigators at Week 13, Week 26, Week 52 and yearly after. At Week 13 and Week 26, responses assessment needs to be confirmed by two serial blood count measurements performed 1-3 weeks apart.

Response is defined as blood counts no longer meeting the standard ("Camitta") criteria (Camitta et al 1975) for severe pancytopenia in SAA, equivalent to 2 of the following values (Scheinberg et al 2009).

- Absolute neutrophil count $\geq 0.5 \times 10^9/L$
- Platelet count $\geq 20 \times 10^9/L$
- Reticulocyte count $\geq 20 \times 10^9/L$

A CR will be defined as (all 3 must be met):

- Absolute neutrophil count $> 1.0 \times 10^9/L$
- Platelet count $> 100 \times 10^9/L$
- Hemoglobin $> 100 \text{ g/L}$

A PR will be defined as blood counts that do not meet criteria for SAA but are not sufficient for a CR.

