### **Time to response**

Time to response is defined as the time from the date of the start of study treatment until the first documented and confirmed response (either CR or PR) per programmatically derived.

Time to complete response is similarly defined as the time from the date of the start of study treatment until the first documented complete response.

All subjects in the FAS will be included in the time to response/CR calculations.

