### **Time to response**

For time to response and time to complete response, if a subject does not meet response/CR before or at the cutoff date, censoring will be performed using the date of the last response assessment.

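### Duration of response: relapse can be dated on any single blood count, but event-free responders are apparently censored back at their last response visit, which biases the curve down at the primary cut-off

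*SAP*

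**What the plan says.** There are two SAPs, one for the primary analysis and one for the final analysis. Both use the same wording for duration of response.

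- **Censoring.** In SAP 2.7.3, complete and partial responders without relapse "will be censored at the date of the last assessment of response with a known outcome". Duration of CR has the same rule. For time to response and time to CR, "censoring will be performed using the date of the last response assessment". Protocol 12.5.1 says of duration of response: "Participant still responding at the cut-off date will be censored at date of last response assessment".
- **When response is assessed.** Protocol 8.3: "Hematologic response assessment will be performed by investigators at Week 13, Week 26, Week 52 and yearly after". Table 8-1 also marks EOT. SAP Table 2-1 has post-baseline windows only for Week 13, Week 26, Week 52, Year 2 and Year 3.
- **What ends a response.** SAP 2.7.1: "Both the responses and the relapse will be programmatically derived". Loss of response counts as relapse if "not explained by any other independent concomitant medical conditions) in one blood count measurements". The triggers are SAA criteria met again, a renewed transfusion requirement, or one low neutrophil or platelet count. Death also ends a response.
- **When counts are taken.** Protocol 8.3 plans them every 4 weeks from Week 26 to the end of eltrombopag (every 2 weeks until the dose is stable), then yearly. Unscheduled counts are allowed, including to look for relapse.
- **Time to response.** SAP 2.7.1 runs it "until the first documented and confirmed response (either CR or PR) per programmatically derived". It does not say which counts can date a response or a CR.

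**The concern.** Kaplan-Meier needs the risk set at each event time to contain everyone still under observation and event-free. Here an event is seen on the blood-count and transfusion clock, while event-free status is credited only on the response-visit clock.

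Take two participants who respond at Week 13. One has a relapse count at Week 40 and contributes 27 weeks and an event. The other reaches the primary cut-off at Week 48 with normal 4-weekly counts, the last at Week 46. That participant is censored at Week 26 and contributes 13 weeks instead of 33. The 20 lost weeks are observed, event-free time.

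Duration of response is a named secondary endpoint. The primary cut-off falls when the last participant reaches Week 26, so many participants will then be between their Week 26 and Week 52 visits.

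**Working it through.** **The plan's own figures.** The documents give no figure for duration of response or time to CR. Their only precision figures are the exact intervals for the CR rate at N = 36. These reproduce: 14/36 gives 23.1-56.5%, 16/36 gives 27.9-61.9%, 18/36 gives 32.9-67.1%, and the maximum half-width is 17.08%. Only the 44% CR rate is used below.

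**Mechanism in a small constructed case.** Ten responders from Week 13. Five are followed past Week 52; the other five would reach the cut-off at Week 48, but one of them relapses at Week 40.
- Censoring at last count: risk set at Week 40 = 10, so S = 1 - 1/10 = 0.90.
- Censoring at last response visit: four have left at Week 26, so the risk set is 6 and S = 1 - 1/6 = 0.83.

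**Simulation at the primary cut-off.**

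Inputs from the documents: 3 participants enrolled by 08-Dec-2020; 36 enrolled, with the last first visit on 03-Dec-2021; cut-off 26 weeks after the last entry; the visit and count schedules above.

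Assumptions not in the documents: the first 3 entered over 10 weeks and the rest uniformly over 52; response onset at Weeks 6-24; constant relapse rate of 5-30% per year; relapse found at the next planned count up to Week 52 and when it occurs after that; no deaths and no early EOT.

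Follow-up then runs 26-88 weeks, and the gap from last response visit to cut-off averages about 14 weeks (90th percentile about 25).

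Rule A censors at the last of Week 13/26/52/104. Rule B censors at the last planned count. Truth is exp(-rate × t/52), with t in weeks from response.

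Relapse-free probability at 39 weeks, large sample:

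| Relapse per year | Truth | A | B | A minus truth (points) |
|---|---|---|---|---|
| 5% | 0.963 | 0.952 | 0.960 | -1.1 |
| 10% | 0.928 | 0.911 | 0.926 | -1.7 |
| 20% | 0.861 | 0.829 | 0.856 | -3.2 |
| 30% | 0.799 | 0.754 | 0.790 | -4.5 |

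At 52 weeks, mean over simulated trials with 24 responders (36 × (0.44 + 0.23) ≈ 24, with 23% partial response (PR) assumed). B2 is rule B with 4-weekly counts continued after Week 52:

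| Relapse per year | Truth | A | B | B2 |
|---|---|---|---|---|
| 5% | 0.951 | 0.894 | 0.902 | 0.951 |
| 10% | 0.905 | 0.794 | 0.808 | 0.901 |
| 20% | 0.819 | 0.641 | 0.663 | 0.808 |
| 30% | 0.741 | 0.543 | 0.571 | 0.730 |

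Rule A is 6 to 20 points low at 52 weeks, but rule B recovers only 1 to 3 of those points. Nobody reaches Week 104 by the cut-off, so under both rules the latest event-free date is Week 52. With response no earlier than Week 6, the longest event-free duration is 52 - 6 = 46 weeks. Beyond that the risk set holds only future relapsers.

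**Time to CR.** Assume 44% CR and 23% PR at Week 26, with 10-40% of the PRs converting to CR by Week 52 and dated on between-visit counts. Non-responders leave efficacy follow-up at Week 26 (Protocol section 3). Truth at 52 weeks with 20% conversion is about 0.44 + 0.23 × 0.20 = 0.486.

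| Conversion | Truth (simulated) | A | B | A minus B (points) |
|---|---|---|---|---|
| 10% | 0.462 | 0.516 | 0.499 | 1.7 |
| 20% | 0.485 | 0.584 | 0.557 | 2.7 |
| 40% | 0.532 | 0.706 | 0.670 | 3.6 |

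Only A minus B comes from the visit rule. The rest (7.2 points at 20%) arises because Week 26 non-responders are censored at Week 26 under either rule.

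**The case against.** **The censoring phrase may not mean the visit.** SAP 2.7.1 bases duration of response on assessments "derived programmatically using laboratory results instead of those reported in the response assessment CRF". On that footing the last assessment could be the last evaluable count, and most of the bias up to about 39 weeks would vanish. Protocol 8.3 describes investigator assessments, which is the source this sentence sets aside. This reading is possible, so the bias is conditional. But the SAP never adopts it for censoring, while Protocol 12.5.1, SAP Table 2-1 and the time-to-response rule point to visits. Two programmers could produce different curves from the same data.

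**The effect is modest.** A simpler simulation (20-24 responders, all responding at Week 13, relapse at 10-40% per year) gives a nine-month shift of 2-5.5 points, about 0.3 to 0.55 of a standard error. Protocol 1.1 reports 80.0% relapse-free at 1.5 years with CsA maintenance, or -ln(0.800)/1.5 ≈ 15% per year, so 10-20% is the more relevant range here. The endpoint is descriptive. This limits the importance, but the error is systematic and cheap to remove.

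**Stronger readings a reader might infer, which the documents do not support:**
- That time to CR is lengthened. The direction is the reverse: CR probability goes up, so time to CR looks shorter.
- That responses, like relapses, are dated on any count. One count is stated to suffice for relapse only.
- That time to any response is materially affected. Week 26 non-responders have no later planned counts, so little bias is expected.
- That responders with a single assessment enter only if they relapsed or died. Protocol 12.5.1 says so, but the SAP has not carried this over.

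**Conclusion.** The concern holds in conditional form. If the last assessment of response is the scheduled or EOT response visit, duration of response is biased down at the primary cut-off: about 1-5 points at 39 weeks for relapse of 5-30% per year, and 6-20 points at 52 weeks, most of which a change of censoring date alone would not repair. The direction was the same in every scenario run. The sizes rest on the assumed relapse, accrual and detection patterns, and leaving out EOT assessments probably overstates them somewhat.

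CR probability after Week 26 is biased up, with about 2-4 points due to this rule if between-visit counts can date a CR.

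The final analysis is much less exposed, because the Year 3 assessment closes most of the duration-of-response gap for completers. It does not repeat time to response (final SAP, section 2.7), so the primary-cut-off result for that endpoint stands alone.

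**What to change.** Use one clock for events and censoring.

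1. In 2.7.3 of both SAPs, censor duration of response and duration of CR at the last date on or before the cut-off on which the participant is documented event-free: the last evaluable blood count, scheduled or unscheduled, with transfusion status known. State that this replaces the last response visit. Transfusion status is needed because a renewed transfusion requirement is itself a relapse.
2. Alternatively, date both events and censoring at scheduled assessments only.
3. In the primary-analysis SAP, apply the same clock to time to CR and state which counts can date a CR. No such edit is needed in the final SAP.
4. Note that estimates beyond about 39 weeks at the primary cut-off remain unreliable, because planned counts become yearly after eltrombopag ends.

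The cost is a few sentences of SAP text and one derived censoring variable. No new data are needed.
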